14.2 Implantation rate in other selections

The point estimate and 95% CI of IR and IR^* will be calculated in the subgroups EC and ENC. No tests of comparison between any subgroup will be conducted.

14.3 KID selection

The same calculations will be conducted for EMG and MG groups and EC and ENC restrained to KID selection.

14.4 Secondary variables selection of ITT

Utilization Rate (UR), Clinical Pregnancy rate (CP), Ongoing Pregnancy rate (OP), Multiple Pregnancy rate (MP), Spontaneous Miscarriage (SM). The estimate and 95% CI will be calculated in both groups EMG and MG, and in both groups EC and ENC.

14.5 Secondary variables KID

The same analysis will be conducted on KID selection for Utilization Rate (UR), Clinical Pregnancy rate (CP), Ongoing Pregnancy rate (OP), Multiple Pregnancy rate

(MP), Spontaneous Miscarriage (SM) . The estimate and 95% CI will be calculated in both groups EMG and MG, and in both groups EC and ENC.

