8.1 Intention-to-treat (Full Analysis Set)

The intention-to-treat population includes all randomized subjects. Due to the fact that this is an exploratory trial in contrast to usual definitions of ITT ('presented as randomized') subjects will be presented based on the method used (EvMG = Eeva scores plus morphology grading, MG=morphology grading only).

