8.3 Added selection

The KID sample (Known Implantation Data) is the subset of ITT sample such that the IR=0% or 100% (for single,double or triple) mbryo transfer, ITT=KID; for other implantations, women such that $0 < IR < 1 < 2 < 3$ will be disregarded).

9 General Specifications for Statistical Analyses

10 Study Subjects

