14.1 Primary analysis

Implantation rate will be analyzed with two definitions

First definition: The IR (at embryo level) corresponding to a group of patients is calculated as the ratio of the total fetal sacs (nFS) identified by ultrasonography at weeks 5 to 8 divided by the number of embryos transferred (nET), thus $IR = nFS/nET$.

Alternative Definition of Implantation Rate: The previous (and usual) calculation of IR as mentioned in the protocol ($IR = nFS/nET$) has problems, in particular the implanted embryos are not independent. The international definition used by WHO in particular (see for instance <http://www.advancedfertility.com/ivf.htm>) is: The alternative definition IR^* at women level is $IR_w = nFS_w/nET_w$ and $IR^* = (1/n) \cdot \sum_{w=1,n} IR_w$.

Note: The two definitions IR and IR^* coincide in some cases, in particular for elective Single Embryo transfer eSET (where only one embryo is transferred) or when KID sample is used, but in the general case (ITT sample for instance, IR and IR^* will be different).

The point estimate and 95% CI of IR and IR^* will be calculated in both groups EMG and MG for the ITT selection. No inferential comparison will be conducted between these two groups (as this study is purely descriptive).

The following sections are considered as secondary analyses.

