Psupp	Protein Supplement	C	4	1= None used, 2 = SPS, 3 = HAS, 4 = SSS, 5 = Other
Negg	N of retrieved eggs	I	6.1	
eggGV	Egg type GV	B		
eggMI	Egg type MI	B		
eggMII	Egg type MII	B		
eggOt	Egg type Other	B		
Trf	Was a transfer attempted ?	B		
Nte	N of transferred Embryos	I	4.1	
Usg	Ultra sound guided	B		1=Yes 2=No
Cat1	Catheter Typ Mucous	B		
Cat2	Catheter Typ Blood	B		
Cat3	Catheter Typ retained embryos	B		
Cat4	Catheter Typ N/A	B		
Grading	Procedure Grading	C	4	1= Easy 2= Difficult
Pdg	Embryo assessed by PGD/PGS	C	4	1=Yes 2=No
Euploid	Euploid transferred ?	B	4	
LPS	Luteal Phase support	B		1=Yes 2=No
DelMet	Delivery Method	C		1= Crinone 2=Endometrin 3=Other Vaginal 4=Intramuscular 5=Other
Test1	Post Transfer test 1	B		1= Urine 2=Blood
Test1r	Post Transfer test 1 result	B		1= Positive 2= Negative
Test2	Post Transfer test 2	B		1= Urine 2=Blood
Test2r	Post Transfer test 2 result	B		1= Positive 2= Negative

US1	Ultra Sound result	B		1= Positive 2= Negative
Nsac	N of gestational Sacs	I	4:1	
Nhbt	N of Heartbeats	I	4:1	
Outc	Final outcome further to Ultra Sound	C		1=No pregnancy 2=Biochemical pregnancy 3=Ectopic 4=miscarriage 5= Ongoing
EndPP	Cycle completed on Per Protocol	B		1=yes 2=o
cycleCSt	IF cycle complete : Status	C		1= Ongoing pregnancy 2= Pregnancy came to term 3= Pregnancy lost 4= Failed to conceive 9= therapeutic abortion 10= Other
cycleNst	If cycle non complete : Status	C		0=Normal 1= OHSS risk 2= Embryo transfer cancelled 5= Freeze all 6= Other 7= Imaging discontinued prior to completion 8= Subject requested to be withdrawn 9= Investigator withdrew subject 10= Subject was lost to follow-up 11= Subject was noncompliant

18 Table description: principles of reporting

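### SAP 14.3 and 14.5 report rates on a KID subset chosen by outcome without saying so, and the SAP 14.1 Note that IR and IR* coincide on KID is not true in general

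*SAP*

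**What the plan says.** SAP 8.3 introduces KID, which "is the subset of ITT sample such that the IR=0% or 100% (for single,double or triple" transfers. Women whose own rate lies strictly between 0 and 100% are disregarded.

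Two sections then use KID:
- SAP 14.3, for IR and IR*: "The same calculations will be conducted for EMG and MG groups and EC and ENC restrained to KID selection".
- SAP 14.5, for the secondary endpoints: "The same analysis will be conducted on KID selection for Utilization Rate (UR), Clinical Pregnancy rate (CP), Ongoing Pregnancy rate (OP), Multiple Pregnancy rate", followed by spontaneous miscarriage (SM), with an estimate and 95% CI in EMG, MG, EC and ENC.

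SAP 14.4 gives the same secondary endpoints on ITT: "Multiple Pregnancy rate (MP), Spontaneous Miscarriage (SM). The estimate and 95% CI will be calculated in both groups EMG and MG", and also in EC and ENC.

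SAP 14.1 defines IR as total sacs over total embryos transferred, and IR* as the mean over women of each woman's own ratio. Its Note says the two coincide for elective single transfer ("where only one embryo is transferred) or when KID sample is used, but in the general case" they differ). For KID the Note sets no condition on the number of embryos transferred (nET). SAP 14.1 plans no inferential comparison and adds: "The following sections are considered as secondary analyses".

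**The concern.** Membership of KID depends on the result being reported. Every failed transfer stays, while every woman dropped for partial implantation has at least one sac. A rate computed on what remains is conditional on outcome and does not estimate the rate in the group.

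The KID tables would carry the same endpoint names, group labels and 95% CIs as the ITT tables, and no section warns the reader. Protocol 5.2 says the trial should yield realistic confidence intervals for planning later trials, so a CI around a different quantity under the same name could be carried forward by mistake.

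The pregnancy endpoints also gain nothing from KID. Clinical pregnancy (CP), ongoing pregnancy (OP), multiple pregnancy (MP) and SM do not require knowing which embryo implanted.

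**Working it through.** **Inputs.** Implantation rates of 25-45% and group sizes of 1000 and 500 come from Protocol 7.2. The KID rule comes from SAP 8.3, and IR and IR* from SAP 14.1. Neither document gives the mix of nET or the within-woman correlation, so both are assumptions. Unless stated otherwise: women with a transfer only, 35% per embryo whatever the nET, independent embryos, and a sac counts as a clinical pregnancy.

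**The plan's own figure.** The half-width in Protocol 7.2 is 1.96·√(p(1−p)/n). At 35% this gives 4.18 (n = 500) and 2.96 (n = 1000), matching the printed 4.2 and 3.0. It serves below as a yardstick.

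**CP.** With p = 0.35, a double transfer gives 0, 1 or 2 sacs with probability 0.4225, 0.455 and 0.1225. KID drops the 0.455. For a share d of doubles, the rest single:
- All transfers: CP = (1−d)·0.35 + d·0.5775
- Kept: k = 1 − 0.455d
- KID: CP = [(1−d)·0.35 + d·0.1225]/k

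| Doubles | Women dropped | CP, all transfers | CP, KID |
|---|---|---|---|
| 0% | 0% | 35.0% | 35.0% |
| 10% | 4.6% | 37.3% | 34.3% |
| 20% | 9.1% | 39.6% | 33.5% |
| 50% | 22.8% | 46.4% | 30.6% |

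At 20% double, the expected KID CI, KID CP ± 1.96·√(CP(1−CP)/(nk)), is 30.4-36.6 (n = 1000) or 29.2-37.8 (n = 500). Neither contains 39.6. With within-woman correlation 0.2 the shift is 38.6 to 33.8. If CP needs a heartbeat, present with probability 0.9 per sac, it is 35.8 to 30.4.

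On KID each woman's ratio is 0 or 1, so CP counted by sacs is the same number as IR*.

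**IR and IR\*.** A dropped double has a ratio of exactly 50%, so removing it lowers any rate below 50%. At 20% double, KID IR is 21.4, 32.3 and 44.0 for true rates of 25, 35 and 45%. With triples, IR and IR* still fall if embryos are independent and the per-embryo rate is the same for every nET. If the rate differs by nET, a very small rise is possible: 95% singles at 45% plus 5% triples at 25% moves IR from 42.27 to 42.32 and IR* from 44.00 to 44.07.

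**MP.** Protocol 6.1 gives no denominator, so both are shown.
- Half single, half double: 6.1 to 7.9% per woman, 13.2 to 25.9% per pregnancy.
- 70/20/10 single/double/triple: 5.3 to 3.4% per woman, 12.2 to 10.5% per pregnancy, because two sacs from three embryos is a multiple pregnancy that KID drops.

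**OP, SM and utilization rate (UR).** Let q be the ongoing rate per pregnancy in KID and q′ that in dropped women. OP falls if q′ > q × (KID CP), that is, if q′ exceeds about 34% of q (20% double) or 31% (half double). A fall is therefore very likely but not forced. SM has no determined direction. UR is not mechanically distorted.

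**Against the ITT table.** SAP 8.1 says: "The intention-to-treat population includes all randomized subjects". SAP 17 lists non-completion codes "2= Embryo transfer cancelled 5= Freeze all 6= Other". If a share u has no transfer and counts as not pregnant, ITT CP is (1−u) times the all-transfer CP. At 20% double it equals KID CP when (1−u)·39.55 = 33.50, so u = 15.3%. At half double, u = 34.1%.

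**The Note.** Take one implanting single and one failed double, both in KID. IR = 1/3 and IR* = (1 + 0)/2 = 1/2. In expectation at half double, IR = (0.5·0.35 + 0.5·2·0.1225)/(0.5 + 0.5·2·0.545) = 0.2975/1.045 = 28.5%. IR* = (0.175 + 0.06125)/0.7725 = 30.6%.

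**The case against.** The strongest reply is that little is hidden and little depends on it. SAP 8.3 states the exclusion openly, SAP 14.5 is headed as KID, everything after SAP 14.1 is labelled secondary, and SAP 19.2.6 plans tables of embryos transferred and sacs by group. All of this stands and limits the severity. It does not tell a reader what the KID rates estimate, and those tables show neither sacs by nET nor the number of women excluded.

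A second reply is that the size rests on an unknown transfer mix. That is correct. With single transfers nothing moves, except that a single embryo giving two sacs has a ratio of 200% and fails the 0%/100% rule. At 10% double the CP shift is 3.0 points, no more than the half-widths in Protocol 7.2. The sentence in SAP 8.3 is also hard to read beyond that rule, so the intended handling of triples is uncertain.

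Three stronger readings are tempting, and the documents do not support them:
- **KID rates always lie below the ITT table.** The fall in CP is certain only among women with a transfer (given at least one failed transfer). Against an all-randomized denominator the direction is open. For IR, IR* and MP it depends on the conditions shown above.
- **KID builds in a false difference between EMG and MG.** That needs a transfer mix or implantation pattern that differs between groups, and the documents give neither.
- **The Note is wrong in every mixed dataset.** If 40% of both the singles and the doubles kept in KID implant, IR and IR* are both 40%.

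**Conclusion.** The point holds as a modest correction to secondary descriptive analyses. KID is selected on outcome, and the CP, OP, MP, SM, IR and IR* reported on it are conditional on that selection, with no statement to that effect. Among women with a transfer, the CP shift at 35% per embryo is 0 with single transfers only, 3.0 points at 10% double, about 6 at 20% and about 16 at half double. These sizes assume independent embryos and the stated mixes. Positive within-woman correlation makes them smaller, and women without a transfer can close or reverse the gap to the ITT table. The Note in SAP 14.1 is false as a general statement when nET is mixed; since SAP 14.3 calculates both rates anyway, this error changes no result.

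A reader might infer that the trial's main result is compromised. It is not: the primary estimates use ITT, and no test is planned on KID.

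**What to change.** 1. Remove CP, OP, MP and SM on KID from SAP 14.5. All four remain on ITT in SAP 14.4. UR may stay or go.
2. Keep KID in SAP 14.3 only as a description of IR, labelled as selected on outcome and not estimating a group rate. Add a table of women excluded from KID, by arm and by nET.
3. Restate the Note in SAP 14.1: IR and IR* coincide when all women have the same nET, or when mean IR does not vary with nET.

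The cost is a few KID tables fewer, one count table more and some SAP wording. No additional data are needed and no endpoint is lost.

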14.6 Exploratory Variables

Multiple Linear regression analysis of IR (based on subject level) as dependent variable and treatment as independent parameter effected by the following confounding factors

Factors	Description
Stimulation protocol	Categorical variable, 3 states: Agonist Luteal phase; Antagonist; and Agonist Mirco-dose Flare and Other
Drugs used	Categorical variable, 3 states: recombinant Gn, urinary Gn, and mix-use of recombinant and urinary Gns
Day of transfer	Categorical variable, 2 states: D3 Vs D5/6
Age of patients	Continuous variable , years
Culture medium	Categorical variable, 5 states: Quinn's Advanced Fertilization, Global Medium, Vitro life G-IVF, Irvine Single Step Medium, and Other

A better estimate of implantation rate will be obtained based on subject level adjusted for confounding factors by a Multiple Linear regression.

Given the exploratory nature of the design, the model will be investigated stepwise and repeated backward. The final model will exclude backward P-values > 0.10.

The Center effect will also to be considered in the model.

The results of regression analysis will be reported with the following items

- Regression Coefficient with 95% CI
- Standard Error
- P-value
- Coefficient of Determination (R^2)

Subgroup analyses

Further subgroup analysis based on selected baseline parameter could be conducted as follows.

- 1) IR of the two treatment groups at each site (descriptive summary statistics with 95% CI,

and RR with 95% CI and P value). The Risk Ratio, 95% CI and P-value will be calculated, provided the number of subjects in a site will be at least 30, otherwise only descriptive statistics will be provided for that particular site.

- 2) IR, CPR, OPR and SMR of the two treatment groups for subgroups of patients with ET on D3 and D5/6 (descriptive summary statistics, RR with 95% CI and P value);
- 3) IR, CPR, OPR and SMR of the two treatment groups for subgroups of patients with age ≤35 and >35(descriptive summary statistics, RR with 95% CI and P value).
- 4) IR of the two treatment groups for subgroups of patients using 5 types of culture media (descriptive summary statistics, RR with 95% CI and P value).
- 5) IR of subgroups of patients using 5 types of culture media (regardless the method of embryo assessment, descriptive summary statistics and 95% CI)

15 Safety Evaluation

In conformity with protocol, device deficiency will be individually listed.

16 References

No reference at this stage

17 Used Variables

In the following table, each variable is characterized by its ID (short name), variable label, type (B=Binary, I=Numerical Integer (such as count), C=Categorical, F=Real Numeric). Format (I.J where I denotes the total number of digits, and J=number of decimals, i:j is a format with j decimals for the tables, but 0 decimal for data list, while i.j denotes j decimals for the tables and data list). The groups of binary variables highlighted in gray will be presented on the same table.

Variable ID	Variable Label	Type	Fmt	Value Labels
Baseline Variables				
Inc<1,13>	Inclusion Criteria	B		
Age	Age	I	6:1	
Preg1	Pregnancy History	B		
Preg2	Number of attempts	I	6:1	
Preg3	Number of Spontaneous abortions	I	6:1	

Preg4	Number of Live Births	I	6:1	
Pt1	N of Non-ART cycles	I	6:1	
Pt2	N of Fresh ART cycles	I	6:1	
Pt32	N of Frozen ART cycles	I	6:1	
FSHm	Folicle Stim Hormone Maximum	F	8:2	
FSHu	Folicle Stimulating Hormone Units	F	8:2	
AMHm	Anti Mullerian Hormone Max	F	8:2	
AMHu	Anti Mullerian Hormone Unit	F	8:2	
E2m	Estradiol Max	F	8:2	
E2u	Estradiol Units	F	8:2	
LHm	Luteinizing Hormone Max	F	8:2	
LHu	Luteinizing Hormone Units	F	8:2	
AFC	Antral Follicle count	I	6:1	
RI1	Male Infertility	B		
RI2	Polycystic Ovaries	B		
RI3	Reduced Ovarian Reserve	B		
RI4	Tubal Factor	B		
RI5	Unexplained	B		
RI6	Other	B		
Prot	Stimulation protocol	C	4	1=Agonist Luteal Phase Start 2=Agonist Micro-Dose Flare 3=Antagonists suppression 4=Other
FSHtd	rFSH (Total Dose)	F	8:2	
FSHnd	rFSH (N of Days)	F	8:2	
LHtd	rLH (Total Dose)	F	8:2	
LHnd	rLH (N of Days)	F	8:2	
FLtd	rFSH-rLH (Total Dose)	F	8:2	
FLnd	rFSH-rLH (N of Days)	F	8:2	
Hmgtd	Hmg (Total Dose)	F	8:2	
Hmgnd	Hmg (N of Days)	F	8:2	
Ufshtd	uFSH (Total Dose)	F	8:2	
Ufshnd	uFSH (N of Days)	F	8:2	
Otttrtd	Other treatments (Total Dose)	F	8:2	
otttrnd	Other treatments (N of Days)	F	8:2	
stimdur	Total number of days of stimulation	I	8:2	

E2pk	Peak estradiol	F	8.2	
E2u	Unit Estradiol	B	4	1=pmol/L 2=pg/mL
Nfol12	N of follicles > 12mm	I	5:1	
Nfol18	N of follicles > 18 mm	I	5:1	
endoth	Endometrium Thickness	F	8.2	
Post Baseline Variables				
Noo	N of oocytes	I	8:1	
Noom	N of Mature oocytes	I	8:1	
Sps	Sperm Sample	C	4	1=Fresh 2=Frozen 3=both
ltype	Insemination Type	C	4	1=ICSI 2=lvf 3= Both
Cult	Culture medium	C	4	1= Quinns Advantage Fertilization 2= Global Medium 3= Vitrolife G-IVF 4= Irvine Single Step Medium 5= Other
Incub1	Incubator Information O2	C	4	1= 5% 2=20%
Incub2	Incubator CO2	F	8.2	
Psupp	Protein Supplement	C	4	1= None used, 2 = SPS, 3 = HAS, 4 = SSS, 5 = Other
Negg	N of retrieved eggs	I	6.1	
eggGV	Egg type GV	B		
eggMI	Egg type MI	B		
eggMII	Egg type MII	B		
eggOt	Egg type Other	B		
Trf	Was a transfer attempted ?	B		
Nte	N of transferred Embryos	I	4.1	
Usg	Ultra sound guided	B		1=Yes 2=No
Cat1	Catheter Typ Mucous	B		
Cat2	Catheter Typ Blood	B		
Cat3	Catheter Typ retained embryos	B		
Cat4	Catheter Typ N/A	B		
Grading	Procedure Grading	C	4	1= Easy 2= Difficult
Pdg	Embryo assessed by PGD/PGS	C	4	1=Yes 2=No
Euploid	Euploid transferred ?	B	4	
LPS	Luteal Phase support	B		1=Yes 2=No
DelMet	Delivery Method	C		1= Crinone 2=Endometrin 3=Other Vaginal 4=Intramuscular 5=Other
Test1	Post Transfer test 1	B		1= Urine 2=Blood
Test1r	Post Transfer test 1 result	B		1= Positive 2= Negative
Test2	Post Transfer test 2	B		1= Urine 2=Blood
Test2r	Post Transfer test 2 result	B		1= Positive 2= Negative

US1	Ultra Sound result	B		1= Positive 2= Negative
Nsac	N of gestational Sacs	I	4:1	
Nhbt	N of Heartbeats	I	4:1	
Outc	Final outcome further to Ultra Sound	C		1=No pregnancy 2=Biochemical pregnancy 3=Ectopic 4=miscarriage 5= Ongoing
EndPP	Cycle completed on Per Protocol	B		1=yes 2=o
cycleCSt	IF cycle complete : Status	C		1= Ongoing pregnancy 2= Pregnancy came to term 3= Pregnancy lost 4= Failed to conceive 9= therapeutic abortion 10= Other
cycleNst	If cycle non complete : Status	C		0=Normal 1= OHSS risk 2= Embryo transfer cancelled 5= Freeze all 6= Other 7= Imaging discontinued prior to completion 8= Subject requested to be withdrawn 9= Investigator withdrew subject 10= Subject was lost to follow-up 11= Subject was noncompliant

18 Table description: principles of reporting

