3.1.1 Risks Related to Eeva

Indeed, there are no risks related with Eeva utilization that could potentially affect embryos survival or quality due to the fact that any malfunction on the Eeva system will only affect its ability to take pictures of the embryos in culture but will not affect in any way the temperature, gas environment and/or culture media conditions to which the embryos will be exposed during the incubation process. In Eeva clinical investigation studies, the average blastocyst formation rate in subjects who had embryo transfers at the blastocyst stage was 47.4%. This demonstrated that embryos imaged by Eeva did not have their development to blastocyst stage altered given the average rate reported in the literature for blastocyst formation is approximately 45.4%.¹⁷

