5.3.1 Inclusion Criteria

For inclusion in the trial, **all** of the following inclusion criteria **must** be fulfilled:

1. All infertile patients treated with IVF/ICSI.
2. Patient age \leq 40 years.
3. \leq 3 failed IVF/ICSI cycles.
4. At least 4 normally fertilized eggs (2PN) in current cycle.
5. Normal uterine cavity.
6. Fertilization using only ejaculated sperm (fresh or frozen).
7. Subject must have read and signed the Informed Consent form.

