5.5 Criteria for Randomization

All eligible subjects will be assigned to the group of subjects with embryo transfers using Eeva scores plus morphology grading and to group of subjects with embryo transfers using morphology grading only by randomization. A permuted block randomization with fixed block size and allocation ratio of 2:1 will be used. Further details of the procedure will be described in the EDC related manuals.

An allocation ratio of 2:1 is used since this is an explorative trial. The main objective is to collect data of first experience with the EEVA Time Lapse system. To generate hypotheses in comparison to the ‘morphology grading only’ group comparable data of the morphology grading only need to be collected.

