7.3 Randomization

Subjects will be assigned to the group of subjects with embryo transfers using Eeva scores plus morphology grading and to group of subjects with embryo transfers using morphology grading only by randomization. A permuted block randomization with fixed block size and allocation ratio of 2:1 will be used. Further details of the procedure will be described in the EDC related Manuals.

An allocation ratio of 2:1 is used since this is an explorative trial. The main objective is to collect data of first experience with the EEVA Time Lapse system. To generate hypotheses in

comparison to the ‘morphology grading only’ group comparable data of the morphology grading only need to be collected.

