8.2 Subject Information and Informed Consent

An unconditional prerequisite for a subject's participation in the trial is his/her written informed consent.

To protect the rights and welfare of trial subjects, the trial will be conducted in conformance with the Declaration of Helsinki and elements of good clinical practices as may be applied to medical devices.^{1,2} The confidentiality provisions within all applicable laws and regulations will apply throughout. Obtaining informed consent in accordance with the policy of the EC, this clinical protocol, and applicable regulations is mandatory for subject participation. The sponsor will avoid improper influence on or inducement of the subject for participating in the trial. The subject informed consent document(s) must be provided in a language that the patient reads and understands. All subjects must provide voluntary, written informed consent prior to the start of any trial-related activities. This includes subjects who are the partners of the subjects, if applicable.

Informed consent should be signed prior to the day of oocyte pick up, preferably on the day of the last ultrasonography for assessment of number of follicles available. On day 1 after oocyte pick up and following assessment of the number of 2PNs available, subjects will either be enrolled in the trial or not included in the trial.

Adequate information must therefore be given to the subject by the Investigator before informed consent is obtained (a person designated by the Investigator may give the information, if permitted by local regulations). A subject information sheet in the local language will be provided by the Sponsor for the purpose of obtaining informed consent. In addition to providing this written information to a potential subject, the Investigator or his/her designee will inform the subject verbally of all pertinent aspects of the trial (*the language used in doing so must be chosen so that the information can be fully and readily understood by laypersons*). Depending on national regulations, a person other than the Investigator may inform the subject and sign the Informed Consent Form.

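### The Day 1 count of normally fertilised eggs (2PN), known before randomisation and already collected, is in no adjustment, subgroup or baseline table of the SAP

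*SAP*

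**What the plan says.** **Entry rule.** Protocol 5.3.1 requires "At least 4 normally fertilized eggs (2PN) in current cycle". No other criterion secures several embryos, and none requires more embryos than will be transferred.

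**Timing.** Under Protocol 8.2, on Day 1 and "following assessment of the number of 2PNs available, subjects will either be enrolled in the trial or not included in the trial". Protocol 5.5 then states: "All eligible subjects will be assigned to the group of subjects with embryo transfers using Eeva scores plus morphology grading". So the count precedes randomisation. This is an inference from the two sections, since neither gives the time of randomisation outright.

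**Allocation.** Protocol 7.3: "A permuted block randomization with fixed block size and allocation ratio of 2:1 will be used". No stratification factor is named; further detail is left to the EDC manuals.

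**Collection.** The total 2PN count is on the retrieval and fertilisation eCRF (Protocol 6.3.2) and among the documented variables (SAP 5.4.2). Normally fertilised oocytes are the denominator of the utilization rate (Protocol 4.2, SAP 5.2).

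**Use.** SAP 14.6 plans "Multiple Linear regression analysis of IR (based on subject level) as dependent variable and treatment as independent parameter effected by the following confounding factors", with five listed factors and a centre effect, reduced backward at P > 0.10. It adds: "Further subgroup analysis based on selected baseline parameter could be conducted as follows". The items are site, day of transfer, age, and culture medium (by arm and pooled). The 2PN count is in neither list. SAP 17 carries the inclusion criteria as yes/no items and has oocyte and egg counts, but no 2PN count. The baseline and retrieval tables (SAP 19.2.3, 19.2.5) also omit it.

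**The concern.** Eeva is used to help choose among a woman's own embryos. Through that choice it can change the implantation rate only where there are more usable embryos than will be transferred. The 2PN count is the pre-randomisation variable closest to that room for selection. Protocol 5.2 wants the trial to produce strong hypotheses for a later RCT, and the women in whom selection is possible matter for that RCT's eligibility and effect size.

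The planned subgroups do not supply this. Age, site and medium do not measure it. Day of transfer is related to it, but is decided after randomisation and may depend on how the embryos develop.

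There is also a balance argument. Protocol 7.5 and SAP 8.1 present women by the method used, not as randomised, so randomisation does not fully protect the comparison. Adjusting for a plausibly prognostic Day 1 count is then useful beyond any gain in precision.

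**Working it through.** **1. The plan's own precision figures.** Protocol 7.2 gives the distance to the 95% limit. With 1.96 × √(p(1−p)/n) and p = 0.35, n = 500 gives 4.18 and n = 1000 gives 2.96 points, against 4.2 and 3.0 printed. All ten cells reproduce to one decimal, so the same formula is used in step 5.

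**2. Inputs for room to choose on Day 5.** Protocol 3.1.1 says "the average blastocyst formation rate in subjects who had embryo transfers at the blastocyst stage was 47.4" per cent, and quotes about 45.4% from the literature. Assumptions: the rate applies to each 2PN embryo, and embryos are independent. With X blastocysts from n 2PN, X ~ Binomial(n, 0.474). There is no choice for a single transfer if X ≤ 1, and none for a double transfer if X ≤ 2.

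For n = 4 the mean is 4 × 0.474 = 1.9, and:
- P(X ≤ 1) = 0.526⁴ + 4 × 0.474 × 0.526³ = 0.0765 + 0.2759 = 0.352
- P(X ≤ 2) = 0.352 + 6 × 0.474² × 0.526² = 0.352 + 0.373 = 0.725

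| 2PN | X ≤ 1 | X ≤ 2 |
|---|---|---|
| 4 | 35% | 73% |
| 5 | 22% | 55% |
| 6 | 14% | 39% |
| 8 | 5% | 18% |
| 10 | 2% | 8% |

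**3. Sensitivity.**
- At 45.4% the row for 4 2PN becomes 38% and 75%.
- With within-woman correlation (beta-binomial, ICC 0.1 to 0.2), that row becomes 38 to 41% and 66 to 69%. At 8 2PN it is 11 to 18% and 26 to 31%.
- Women with no blastocyst have no Day 5 transfer and add nothing to the rate. Excluding them at 4 2PN gives (0.3525 − 0.0765)/(1 − 0.0765) = 29.9% for single and (0.7255 − 0.0765)/(1 − 0.0765) = 70.3% for double transfer.
- The documents give no 2PN distribution. Under three assumed distributions truncated at 4 (means 7.2, 8.7 and 10.3), the overall Day 5 no-choice share is 15%, 11% and 8% for single and 37%, 28% and 22% for double transfer.

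**4. Dilution, for illustration.** Assume a gain of 6 points where there is a choice and none elsewhere; the 6 is not from the documents. The average gain is 6 × P(choice):
- 4 2PN: 6 × 0.648 = 3.9 (single), 6 × 0.275 = 1.6 (double)
- 8 2PN: 6 × 0.952 = 5.7 (single), 6 × 0.819 = 4.9 (double)

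The contrast between 8 and 4 2PN is therefore 1.8 or 3.3 points.

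**5. What a 2PN table could show.** Assume a 35% rate, one embryo per woman, 500 and 1000 women, and 30% in the low band (150 and 300, against 350 and 700). The 95% half-width of the arm difference is:
- overall: 1.96 × √(0.2275 × (1/500 + 1/1000)) = 5.1 points
- low band: 1.96 × √(0.2275 × (1/150 + 1/300)) = 9.3 points
- high band: 1.96 × √(0.2275 × (1/350 + 1/700)) = 6.1 points
- difference between bands: √(9.35² + 6.12²) = 11.2 points

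For comparison, SAP 14.6 allows a site risk ratio and P value from 30 women. Split 20:10 at 35%, the half-width of the arm difference is 1.96 × √(0.2275 × (1/20 + 1/10)) = 36 points.

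**The case against.** **The primary analysis is descriptive.** SAP 14.1 rules out an inferential comparison, and 14.6 is exploratory. Averaging over all enrolled women is a legitimate estimate for that population; dilution is not bias. This stands, and it keeps the point modest. But 14.6 still plans a treatment coefficient with a P value and subgroup risk ratios, and a 2PN covariate and table fit within that.

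**A reader might infer that the entry rule often fails, or that Eeva cannot help women near the threshold.** The documents support neither. The 35% and 73% are for exactly 4 2PN and a Day 5 transfer; the documents give no 2PN distribution and no Day 3/Day 5 split. Eeva results are read on Day 3, when each embryo's fate is recorded (Protocol 6.3.3), so a woman with 4 2PN and a Day 3 transfer may still have several embryos to rank. The 47.4% is an average among women who reached blastocyst transfer, with no denominator stated.

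**The SAP already plans a Day 3 versus Day 5/6 subgroup and lists 2PN as documented.** Both are true. The first is a post-randomisation split. The second does not put the count into any listed table or model.

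**The remedy cannot settle the question.** Largely right. A main-effect covariate neither reveals nor removes dilution. The banded contrast has a half-width of about 11 points, against an illustrative difference of 2 to 3. Nor do the documents show that 2PN predicts implantation, so no gain in precision can be quantified.

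**Conclusion.** The omission is confirmed: a pre-randomisation variable that is collected and is the denominator of a secondary endpoint appears in no covariate, subgroup, variable or baseline list. It is worth correcting, at modest weight in an exploratory trial.

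The case for including it rests on two things: it is the baseline measure of room for selection, and the arms are formed by method used. The Day 5 figures (35% and 73% at 4 2PN, 5% and 18% at 8) assume the protocol's blastocyst rate per 2PN embryo and independence. They show that choice may be limited near the threshold, not how often this happens in the trial.

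A reader might also infer that a 2PN table would separate a null average from a benefit confined to women with more embryos. With intervals of this width it would not. It can only describe where any difference lies and inform the next trial.

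**What to change.** Leave eligibility and data collection unchanged, and amend the SAP before database lock:

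1. **SAP 17 and 19.2.3:** add the Day 1 2PN count as a baseline variable, tabulated by arm. This also supplies the utilization-rate denominator.
2. **SAP 14.6, regression:** include the count as a pre-specified covariate that stays in the model whatever its P value, exempt from the backward step. Give the reasons as precision and balance between arms formed by method used.
3. **SAP 14.6, subgroups:** add one descriptive table of IR, IR* and clinical pregnancy by arm in 2PN bands fixed before lock (for example 4–5, 6–8 and 9 or more), with the arm-by-2PN estimate and its 95% CI. State that the interval will be wide (about ±11 points under an assumed 30/70 split) and that the table is hypothesis-generating only.

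The cost is SAP wording, one baseline row and one extra table. The downside is one more exploratory subgroup.
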